4.1 OVERVIEW OF STUDY DESIGN/INTERVENTION

4.2 Design

This study is proposed to be carried out across a two year period including an intervention period and dissemination of results to the Taxi Network community. Twenty eight non-smoking male NYC cab drivers will be recruited and randomized to one of two study arms, an Intervention Group (to receive the HEPA filter 2 weeks into their 4 week period of participation) and a Wait-list Control Group (to receive the HEPA filter at the end of their 4 weeks of participation). For the Intervention and Wait-list Control Group drivers, during the first 2 weeks, measurements (e.g. biological markers and air monitoring) will be taken under usual conditions. At the end of the initial two weeks, portable HEPA air purifiers (136) will be placed in the Intervention Group drivers' cars and the air monitoring and biological parameters will be repeated for another 2-week period, to determine changes in PM levels and physiological measurements as a result of this targeted intervention. The Wait-list Control Group drivers will not receive a HEPA air purifier at this time, but will also have the air monitoring and biological parameters repeated for another 2 weeks. At the end of the 1 month period of measurements for both groups of drivers, the Wait-list drivers will then receive a HEPA air purifier, so that they may also potentially benefit from the intervention being tested in this study, but no further measurements will be taken. Drivers will serve as their own controls before/after work and before and after the intervention.

Our taxi network CAB (Community Advisory/Action Board) will be engaged in the implementation and dissemination of the proposed study. This Taxi CAB represents the full range of the taxi driver experience, including varied shifts, income, education, age, ownership/lease arrangements, and countries of origin. The Taxi CAB will be instrumental in study recruitment and dissemination of results. The CAB will meet quarterly, with additional meetings as needed. This study is conducted in collaboration with Drs. [name] and [name]'s research teams at New York University Department of Environmental Medicine, and [name], working from the City College of New York (CCNY). Biological specimens collected will be immediately transported to MSK BAIC Core facilities for temporary storage and will be shipped later to either NYU or CCNY (outlined in the assessment and evaluation-section 7).

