4.3 Intervention

Over the course of the study, we will monitor several biological and physiological markers associated with lung cancer and CVD risk, along with ongoing air monitoring of work-sites and residences of all study participants. HEPA filters were selected as the intervention because of their effectiveness in removing PM and volatile organic compounds (VOCs), ease of use, relatively low-cost, small size, light weight, and lack of interference with drivers' normal practices (136). In a previous study by Pui et al., placing the air recirculation mode on (and with a cabin air filter in place already installed by the car manufacturer, not all cars have cabin air filters), was successful at substantially removing ultrafine particles, although was still relatively inefficient (45.5% particle removal efficiency) compared to a HEPA filter (137).

The study will require 4 weeks of participation. Drivers will be recruited and randomized to either the control condition or the HEPA filter intervention condition. The in-vehicle (for all drivers PM exposure levels and physiologic and biochemical markers will be measured over the course of 1 month. For the first two weeks of the 1-month period, measurements will be taken under usual conditions (*without HEPA filters*) for all participants.

Particulate matter concentrations will be measured/monitored through *Personal DataRams* (pDR) (*personalDataRam*[™] model pDR-1200). The DataRam measures particulate matter through optical impedance, and produces per-minute averages. Therefore, the time that the DataRam is —onll will be directly reflected in the data that is produced. The pDR is 24 ounces, 6.3 inches in height, 8.1 inches in width, and 2.4 inches in depth, and is thus very portable. One pDR will be provided to each enrolled participant. All participants will monitor PM at their homes in the room in which they spend most of their off work hours; the DataRam will then be moved to the bedroom at night (or during sleeping hours). For drivers, the pDR will record PM levels throughout the work shift while the vehicle is in motion, momentarily stopped, or parked.

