Black carbon exposures will be measured/monitored through BGI 400 Personal Sampler Pump. The BGI pump is a constant air flow sampler that has broad applications in industry hygiene and environmental testing. It is compact, 6.75 inches in height, 3.1 inches in width and 2.3 inches in depth, which is ideal for mobile projects. It is attached to an external

Nickel Metal Hydride battery, which is 5.75 inches in height, 3.60 inches in width and 1.10 inches in depth. BGI pump connects with a Tygon or ID tubing, ¼ inch in diameter, which is attached to a plastic cassette on the other end, where the pre baked quartz filter is placed. The BGI pump and filter will be placed in the vehicle of the participant at the beginning of their work shift and picked up at the end of their shift. All participants will monitor black carbon exposures at minimum for one work shifts on week 1 and week 4 of the study, or a maximum of three work shifts every week.

PAH exposure will be measured through portable passive Polyurethane Foam Filter (PUF) sampler sized 10 cm by 2.2 cm diameter (171). The PUF filter will be place in the vehicle of the drivers at the beginning of their work shift and picked up at the end of their shift. Drivers will monitor PAH through PUF sampler one day every week.

The intervention of HEPA air filters will be introduced after 2 weeks of participation in the Driver Intervention group (but not in those of the control drivers' cars. The HEPA air purifier is 7.5"x 8.5", 6 lb, and covers up to 150 sq feet. An accompanying auto adapter kit contains a cigarette lighter adapter, 7 foot cord, and a seatbelt clip to secure the filter (159). Air monitoring and measurements of PM exposure levels and physiologic and biochemical markers will be continued for another 2-week period to assess the extent of risk reduction achieved by this targeted intervention. Two weeks should be more than sufficient to measure risk reduction by the HEPA filter intervention, as the study by Pui et al. showed that with the air recirculation mode on and a cabin filter in place, in-cabin aerosol concentration was reduced to below typical office air concentrations in approximately 3 minutes (137). HEPA filters will be given to drivers in the Wait-list Control Group at the end of the 4 weeks of participation.

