Feasibility data will be collected to inform the conduct of a large scale randomized controlled trial assessing the impact of the HEPA filter intervention on reducing PM exposure and associated physiologic and biochemical markers. We will document the number of individuals approached for participation, the number refusing and reasons for refusal. We will document the time spent and the number of attempts to contact participants by phone and to meet in person. We will document adherence with study protocol, i.e. taking the dataRAMS to and from home and work, completing the multiple biological measurements. We will document the time spent conducting the study measurements. We will document dropout rates and reasons for drop out.

PARAMETERS-TIME POINTS*	At Intake	At Half-Way Point	1 Work Day per Week	1 Non-Work Day per week	1 work day (wk 1 & wk 4)	Every Day
Epigenetic Changes	X					
Hs-CRP	X					
Salivary Cotinine	X	X				
Serum Cytokines					X	
White blood cell profile					X	
Blood Pressure			X	X		
Heart rate variability						X
PM/Air Pollution						X
1-hydroxypyrene					X	
Black carbon			X			
PUF sample			X			

* Study Period = 28 Days

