9.1 PRIMARY OUTCOMES

The primary outcomes are:

- To collect preliminary data on in-vehicle excess PM exposure the personal DataRam will monitor/report the PM levels as time-averaged sample (hourly averages) that will be monitored at work site and at homes across all groups
- To conduct a preliminary assessment of the correlation between PM exposure and physiologic and biochemical markers associated with increased risk of lung cancer and CVD the personal DataRam will monitor/report PM levels (hourly averages) that will be analyzed in comparison to increased systolic blood pressure, reduced heart rate variability, and presence of biological markers related to lung cancer and CVD risk.

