11.0 BIOSTATISTICS

Overview. This pilot study follows a two parallel arm design. Drivers will be randomized to one of two groups, an Intervention Group (an in-vehicle HEPA filter will be provided) and a Wait-list Control Group (HEPA filter will be provided at the end of wait-list period). We plan to recruit a sample of n=14 participants in each group (n=11 per arm with analyzable (non-missing) data, assuming a 25% drop-out rate as described below).

General analytic strategies. The general data analytic paradigm for this pilot study will be descriptive statistics only. The aim is to collect pilot data to help guide a future randomized intervention study. Descriptive statistics and assessments of correlations will be sought to address the aims (see below). The sample size of 14 per condition was primarily determined by resources limitations. A sample of 14 per condition was deemed possible within the funding resources of no more than 2 years.

Analytic plans for the Specific Aims.

Aim 1a: The primary aim will be to collect preliminary data on in-vehicle excess PM exposure.

Descriptive statistics (means and standard deviations) will be sought on: 1) PM size distribution 2) mass concentration, and 3) chemical composition for all three groups. These observations will be used to evaluate to what extent the two groups were exposed to these environmental hazards. For each study participant, an area-under-the-curve (AUC) summary will be sought for each of the three PM measurements over appropriate time periods. Generally, a daily average will be calculated from the hourly PM assessments. Then the AUC of the 28 daily averages will be calculated per person to represent the summary of PM exposures during study participation.

Aim 1b: To conduct a preliminary assessment of the correlation between PM exposure and physiologic and biochemical markers associated with increased risk of lung cancer and/or CVD.

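### The only window given for the Aim 1a PM summary is a 28-day AUC, which in the Intervention arm blends 14 usual-condition days with 14 days after the HEPA purifier is installed

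*Combined protocol and SAP*

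**What the plan says.** Section 11.0, Aim 1a, plans means and SDs of the PM measures, followed by a per-person AUC. Daily averages are formed from the hourly readings, and then: "Then the AUC of the 28 daily averages will be calculated per person to represent the summary of PM exposures during study participation". The assessment table in Section 7.1 confirms the length: "Study Period = 28 Days".

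The filter starts inside that window in one arm only. Section 4.3 states: "The intervention of HEPA air filters will be introduced after 2 weeks of participation in the Driver Intervention group". For the other arm it states: "HEPA filters will be given to drivers in the Wait-list Control Group at the end of the 4 weeks of participation". Section 4.3 also identifies the filter-free period common to everyone: "For the first two weeks of the 1-month period, measurements will be taken under usual conditions".

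The first primary outcome in Section 9.1 concerns the same subject: "To collect preliminary data on in-vehicle excess PM exposure the personal DataRam will monitor/report the PM levels". The reporting unit there is the hourly average, at work and at home. The AUC is not mentioned.

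Two pieces of wording leave some room. The sentence in Section 11.0 that introduces the AUC says it will be taken over suitable periods, which it does not define. Under Aim 1b, a first-week AUC paired with first-week cytokines is given as an example, with the linkage to be settled after the data are in.

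**The concern.** Aim 1a asks how much excess PM taxi drivers meet in their vehicles, and Section 11.0 intends the figures to show how far each group was exposed to an environmental hazard. Aim 2 separately asks whether the filter lowers PM. A single 28-day summary places the Aim 2 effect inside the Aim 1a figure for half the drivers.

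Three things follow if the plan is carried out as written:

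- The Intervention-arm mean depends on how well the purifier works and how often it is switched on.
- The between-driver SD in that arm includes differences in filter effect. Planners of the larger trial could mistake it for natural variation in exposure.
- A difference between arms on this summary would be a diluted filter effect, not a difference in occupational hazard.

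The point carries into Aim 1b, which correlates the markers with the Aim 1a AUCs. Buccal methylation is sampled only at Intake. In the Intervention arm it could therefore be set against an exposure figure half of which comes from later, filtered days.

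**Working it through.** **Inputs from the documents.** Window: 4 weeks × 7 = 28 daily averages, which reproduces the plan's figure. Filter start: after 2 × 7 = 14 days (Intervention), after day 28 (Wait-list). Time in the cab: 10-12 h per shift on about 6 days a week (Section 3.0), so 60-72 of 168 h per week. Sample: 14 per arm with 25% drop-out, 14 × 0.75 = 10.5, taken as 11 per arm.

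**Assumptions.** The in-cab reduction *e* achieved by this HEPA unit is not stated; I use 0.20 to 0.90, with 0 as the no-effect case. The cab-to-home PM ratio *R* is not stated; I use 1 to 3.

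**Cab-only PM.** Set usual daily exposure to 1. The Intervention series is fourteen values of 1, then fourteen of 1 − *e*. By the trapezoid rule its AUC is 13 × 1 + (1 − *e*/2) + 13 × (1 − *e*) = 27 − 13.5*e*, against 27 for an unfiltered series. The shortfall is 13.5*e*/27 = 0.5*e*; a simple sum over 28 days gives the same.

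| Assumed reduction *e* | Intervention arm | Mean over two equal arms |
|---|---|---|
| 0 | 0% | 0% |
| 0.20 | 10% | 5% |
| 0.70 | 35% | 17.5% |
| 0.90 | 45% | 22.5% |

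The Wait-list arm is at 0% in every row.

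**Daily averages that include home hours.** Section 11.0 does not restrict the daily average to work hours, so home readings may enter. With *h* hours per shift, the cab's share of weekly exposure is *s* = 6*hR* / (6*hR* + 168 − 6*h*), and the shortfall is about 0.5 × *e* × *s*.

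- *h* = 10, *R* = 1: *s* = 60/168 = 0.357. The shortfall is 3.6% at *e* = 0.20 and 16.1% at *e* = 0.90.
- *h* = 12, *R* = 3: *s* = 216/312 = 0.692. The shortfall is 6.9% at *e* = 0.20 and 31.2% at *e* = 0.90.

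A day-by-day trapezoid with every seventh day off work gives slightly more: 3.7% to 7.1% at *e* = 0.20, and 16.7% to 32.1% at *e* = 0.90. The full range is therefore about 4% to 32%.

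**Spread.** If driver *i* has usual exposure *m* and filter effect *e* (each varying by driver), the cab-only daily mean over 28 days is *m* × (1 − 0.5*e*). Variation in *e* therefore enters the SD.

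**Days 1-14 only.** The shortfall is 0% in both arms for any *e*. All 28 drivers, about 22 of them analyzable, then contribute filter-free data. With the 28-day AUC only the Wait-list arm, about 11 analyzable, does so.

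**The case against.** The strongest reply is that the AUC's stated purpose is to summarise exposure over the period of participation, and for that quantity it is exact. This stands. The AUC is low only relative to usual exposure, and only if the filter works, which is the question in Aim 2.

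A reader might go further and infer that the first primary outcome is itself biased low. The documents do not support that. Section 9.1 defines the outcome by hourly averages and does not name the AUC. Section 11.0 also lists means and SDs without saying that they are computed from the AUC.

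A reader might also attach a firmer size to the shortfall using figures in the background text. Neither figure fits. The 3-5 ratio in Section 3.0 compares in-vehicle with outdoor air, not with homes. The 45.5% in Section 4.3 is for a manufacturer's cabin filter with recirculation acting on ultrafine particles, and is cited there as inefficient compared with HEPA.

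The open wording about periods, and the first-week example, show that shorter windows were foreseen. They permit a pre-filter summary but do not commit to one, and the example belongs to Aim 1b. The only window actually specified for Aim 1a is 28 days.

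Finally, the analysis is purely descriptive, the Wait-list arm is clean, and the time-stamped data would allow a days 1-14 figure at any time. That limits the harm: no alpha or power figure is touched. It does not remove the point, because in a descriptive pilot the descriptive figures are the product.

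**Conclusion.** The point holds in a limited form. As written, the per-person Aim 1a summary mixes 14 usual-condition days with 14 post-installation days in the Intervention arm, and nothing in the Aim 1a text separates them. Read as usual occupational exposure, it is understated in that arm by half the filter's in-cab effect, or by less once home hours are averaged in, and its SD is affected as well. The mechanism follows from the documents. The percentages rest on the assumed filter effect and cab-to-home ratio, and they vanish if the filter has no effect. The plan should be changed, but this is a matter of defining the summary and not a flaw in the trial's design or data collection.

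**What to change.** In Section 11.0:

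1. **Aim 1a:** define the usual-exposure summary as a per-day average (or AUC) over days 1-14 in both arms, reported over all drivers and by arm.
2. **Aim 2:** summarise days 15-28 separately by arm.
3. **Aim 1b:** keep time-matched AUCs from any week available, including weeks after the filter starts. Section 7.1 schedules cytokines, white-cell profiles and 1-hydroxypyrene in week 4 as well as early in the study, and those markers need week-4 exposure. Confining the Intervention arm's later days to Aim 2 would remove it.
4. **28-day AUC:** keep it, if wanted, as a secondary description labelled as exposure during participation.

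No new data are needed, because PM is logged daily with time stamps. The cost is a few sentences across three aims and a shorter window per driver in the Aim 1a summary: 14 days instead of 28, including for Wait-list drivers, whose later days are also filter-free.

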For each group, a correlation matrix will be constructed between the three components of the AUC outcomes described in Aim 1a and a set of physiologic and biochemical markers. Generally, Pearson's correlation coefficients will be sought. If preliminary analyses found the variables to be skewed, then Spearman's rank correlation coefficients will be calculated instead. The purpose of these correlation coefficients are to examine the associations between the environmental exposure to air pollutants and physiologic and biochemical markers. Point-biserial correlation coefficients will be sought between the continuous AUC summaries of PM data and other binary variables of interest (e.g., methylation). These correlation coefficients can be sorted in descending order to help identify the top candidates of physiologic and biochemical markers that are most likely to be associated with PM exposure. Care will be taken to match the variables by time, using the time stamps from the PM measurements and the date of biomarker serum collection. For example, the AUC of PM in the first week will be associated with serum cytokines measured during the first week. This work will have to be done in a post-hoc manner, after we have all data sources. Then we will evaluate the best strategies to link them together by time. It helps to have automatic time stamps by the PM measurement devices, which is likely to minimize coding errors and missing data.

Aim 2: To use a randomized wait-list controlled design to conduct a pilot study of whether a targeted intervention, installation of a portable car high-efficiency particulate air (HEPA) filter (to remove PM), results in a reduction of in-vehicle PM exposure and associated physiologic and biochemical markers among taxi drivers..

We will calculate the difference in the three PM components and in physiologic/biochemical markers between the HEPA intervention condition and the Wait-List Control condition to obtain the pilot data needed for a future, larger study with the potential to provide remediation to potential harmful exposures to air pollution among NYC taxi drivers.

Aim 3: To collect feasibility data on conducting the proposed randomized wait-list controlled pilot study among New York City taxi drivers.

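### The 28-day PM summary is not divided by time observed, and it mixes cab with home hours and pre-filter with post-filter weeks

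*Combined protocol and SAP*

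**What the plan says.** Section 11.0, Aim 1a, builds the exposure summary in two steps. First, "Generally, a daily average will be calculated from the hourly PM assessments". Then, "Then the AUC of the 28 daily averages will be calculated per person to represent the summary of PM exposures during study participation". The same paragraph leaves the window partly open: "an area-under-the-curve (AUC) summary will be sought for each of the three PM measurements over appropriate time periods". Under Aim 1b these summaries are correlated with the physiologic and biochemical markers, and one shorter window is given as an example: "the AUC of PM in the first week will be associated with serum cytokines measured during the first week". How exposure and markers are linked in time is otherwise to be settled after the data are in.

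The Overview of Section 11.0 plans 14 drivers per arm and "n=11 per arm with analyzable (non-missing) data", "assuming a 25% drop-out rate as described below". Nothing later in that section says how drop-outs enter the analysis. The footnote to the schedule in Section 7.1 reads "Study Period = 28 Days".

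The monitor travels with the driver, in the cab during shifts and at home otherwise (Sections 4.3 and 7.1). Section 4.3 says that the time it is switched on "will be directly reflected in the data that is produced". Monitor adherence, drop-out and missing data are to be documented (Section 7.1, Feasibility Data; Section 11.0, Aim 3; Section 13.2), but none of these feeds into the AUC. The documents give no AUC formula, no minimum hours per day or days per driver, no treatment of gaps or early stopping, and no division by monitored time.

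**The concern.** A total grows with the length of observation. If a driver who leaves early is kept with the AUC he has accumulated, his score falls because he left, not because his air was cleaner. If he is left out, his valid early weeks are lost.

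Two further features of the summary work against the aims. Averaging over the whole day pools cab and home hours, whereas Aims 1a and 2 concern in-vehicle PM. Running over 28 days pools the two weeks before the filter with the two weeks after it in the intervention arm.

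The AUC enters the Aim 1b correlations, and the relation between PM and markers is one of the primary outcomes in Section 9.1. Those correlations are to be ranked to pick candidate markers for the next trial. The study is descriptive, so no significance level or power is affected. What is at stake is whether the pilot estimates mean what they are taken to mean.

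**Working it through.** **Step 1. The plan's own figure.** 14 × (1 − 0.25) = 10.5, rounded up to 11 per arm. This reproduces, so about 14 − 11 = 3 drivers per arm are expected to be incomplete.

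**Step 2. Early stopping.** Let the concentration be a constant C and the last logged day be k. A plain sum of daily averages gives C × k, against 28C for a completer. The trapezoid rule gives C × (k − 1), against 27C.

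| Last day | Sum, k/28 | Change | Trapezoid, (k − 1)/27 | Change |
|---|---|---|---|---|
| 7 | 0.250 | −75.0% | 0.222 | −77.8% |
| 14 | 0.500 | −50.0% | 0.481 | −51.9% |
| 21 | 0.750 | −25.0% | 0.741 | −25.9% |

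The percentages do not depend on C. They can reverse ranks: a driver at 40 µg/m³ who stops after day 14 scores 40 × 13 = 520 by the trapezoid rule, below a completer at 21 µg/m³ with 21 × 27 = 567. Spearman's coefficient, the plan's fallback for skewed variables, does not repair a reversed rank. Divided by time observed, the scores are 40 and 21.

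**Step 3. Missing days in the middle.** Three missing days lower a plain sum by 3/28 = 10.7%, and seven lower it by 7/28 = 25%. A trapezoid AUC bridges the gap and changes by 0% at constant PM.

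**Step 4. Missing hours within a day.** The daily average is the mean of the hours recorded. The home PM level is not in the documents, so the concentrations here are assumptions, with a 12-hour shift.

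- Cab 25, home 10 µg/m³: the full day is (12 × 25 + 12 × 10)/24 = 17.5. Losing all home hours gives 25 (+43%). Losing all shift hours gives 10 (−43%).
- Cab 10, home 20 µg/m³: the full day is 15. The same losses give 10 (−33%) and 20 (+33%).
- Half of both shift and home hours lost: 0% change in either case.

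**Step 5. A scale for comparison.** Suppose the filter halves cab PM in weeks 3-4. The 28-day AUC of a driver with complete data then falls by 0.5 × (14/28) × s = 0.25s, where s is the cab's share of the total. Take 6 shifts a week, so that 168 weekly hours split into shift and other hours, and an assumed cab-to-home ratio r.

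- 10-hour shifts, r = 1: s = 60/168 = 0.357, a fall of 8.9%.
- 12-hour shifts, r = 5: s = (72 × 5)/(72 × 5 + 96) = 0.789, a fall of 19.7%.

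In a mean over shift hours in weeks 3-4 the same effect would appear as 50%. Losing the last week of monitoring (25%) exceeds the filter signal in the AUC throughout this assumed range.

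**Step 6. Effect on a correlation (simulation, assumptions only).** With n = 14, a true correlation of 0.5 between log PM and a marker, 25% drop-out on a random day, and a log-SD of PM of 0.3, 0.5 or 0.8, the mean Pearson coefficients are:

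| Summary used | 0.3 | 0.5 | 0.8 |
|---|---|---|---|
| Complete data | 0.478 | 0.463 | 0.443 |
| Truncated AUC, drop-outs kept | 0.342 | 0.383 | 0.401 |
| AUC divided by time | 0.478 | 0.463 | 0.443 |
| Completers only | 0.472 | 0.461 | 0.446 |

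When drop-out is random, excluding drop-outs costs data but hardly moves the mean coefficient. Keeping them with truncated totals attenuates it.

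**The case against.** The best defence is that the stated rule concerns 28 daily averages. When all 28 exist, it ranks drivers essentially as their mean does, so for completers the missing divisor does no harm. What happens with fewer than 28 is unstated rather than wrongly stated, and the reference to analyzable, non-missing data may mean that incomplete drivers are simply left out. That stands as far as it goes, but the phrase is a recruitment-planning line and not a defined analysis set. If it is the rule, the valid early data of about 3 of 14 drivers per arm are lost. The two harms are alternatives: one driver cannot suffer both.

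A second defence is that shorter windows are allowed. A first-week AUC is untouched by someone leaving at day 14 or 21, which limits the effect for Aim 1b. But a shorter total keeps the same dependence on days logged: two days lost from a seven-day sum lower it by 2/7 = 29%. Means and standard deviations are also planned under Aim 1a, so the AUC is not the only PM description.

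A reader might infer that every hour or day with the monitor off makes a driver look less exposed. The documents do not support this. Hours are averaged within the day first, so lost hours can move the value either way or not at all (Step 4), and interior gaps need not lower a trapezoid AUC (Step 3). Nor does the Section 4.3 sentence on monitor-on time say that the AUC scales with it. If anything, it indicates that monitored time will be known.

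**Conclusion.** The point holds in this form: the AUC of 28 daily averages is not divided by time observed, and no rule covers incomplete monitoring. A driver retained after stopping at day 21 or day 14 scores about 25% or 50% low at constant concentration. Excluding him wastes his earlier weeks. Partly logged days distort the daily average in a direction that depends on which hours are lost and on whether cab or home is dirtier. Even for completers, the summary blends cab with home and, in the intervention arm, pre-filter with post-filter weeks.

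The early-stopping figures assume constant PM and nothing else. The 9-20% comparison assumes a halving of cab PM, 6 shifts a week and a cab-to-home ratio of 1 to 5. The documents give no home level, and a cab cleaner than home is not covered by that range.

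A reader might go further in two ways that the documents do not support. One is that the arm comparison is certainly made on the AUC. Aim 2 speaks of the three PM components, which may be the same summaries, but it does not name the AUC. The other is that logging differs between arms. In an open-label study that is possible, but nothing shows it.

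**What to change.** In Section 11.0, replace the 28-day AUC with a time-weighted mean concentration computed directly from the hourly monitor values: the sum of valid hourly values divided by the number of valid hours.

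- Compute it separately for shift and home hours, and for weeks 1-2 and weeks 3-4. For Aim 1b, use the week matched to the marker.
- Use the shift-hour means for the Aim 2 arm comparison.
- Set a minimum number of valid shift hours before the data are examined.
- Include every randomised driver with enough valid hours in the period, and report hours logged by arm.

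Start from the hourly values. Dividing the existing AUC of daily averages by hours logged would over-correct: a driver who logs half the hours each day would score double.

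The cost is about a paragraph of text and a little analysis work on time-stamped data already planned. The shift/home split needs shift start and end times. The description of the log-book in Section 7.1 does not list them, so check that Appendix C or another record captures them. The downside is that means from drivers with few logged hours are noisier, which the minimum and the reported hours make visible.
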